4.3 Justification for Protein Dose Levels

Dose levels are based on data from previous studies with AF03 for Sanofi Pasteur’s Influenza vaccine products, a study done with Sanofi Pasteur-manufactured monovalent H7N9 influenza vaccine adjuvanted with AS03 or MF59 (38), and on studies done with Panblok H7 adjuvanted with AS03 and MF59. Additionally, formulations of SARS candidates and recently reported data from candidate SARS-CoV-2 vaccines that were developed and tested preclinically informed the range of antigen dosing that was considered.

- For Sanofi Pasteur’s pandemic influenza vaccine projects, the main doses evaluated with H1 and H5 antigens adjuvanted with AF03 were 3.8 µg, 7.5 µg, and 15 µg.
- For monovalent H7N9 influenza vaccine, 2 doses of 3.75 µg, 7.5 µg or 15 µg of H7 antigen adjuvanted with AS03 were compared to a variety of other formulations and vaccine combinations, including 2 doses of 45 µg of H7 antigen alone.
- For Panblok H7, the doses evaluated in Study BP-I-17-002 with MF59 and AS03 were: 3.75 µg, 7.5 µg, and 15 µg.
- For Protein Sciences’ SARS-CoV dTM S protein vaccine, the doses evaluated with or without Alhydrogel® were 5 µg, 15 µg, and 45 µg.

- A recombinant prefusion stabilized SARS-CoV-2 S protein vaccine manufactured in baculovirus expression system was tested in non-human primates at doses of 1 µg, 5 µg, and 25 µg, delivered with a proprietary adjuvant (39).
- An inactivate whole virus SARS-CoV-2 candidate vaccine adjuvant with Alum was tested in non-human primates at doses of 2 µg and 8 µg per dose (40).

It is unknown how immunogenic the CoV2 preS dTM vaccine will be compared to recombinant influenza antigens. Assuming conservatively that it will be weakly immunogenic, the responses following administration of H7 Panblok with MF59 and AS03 are informative. H7 (in common with H5) is weakly immunogenic (13) (14) and could frame dosing expectations under this conservative assumption.

The homologous and heterologous seroprotection (hemagglutination inhibition [HAI] titer \geq 1:40) rate responses at D50 to H7 with MF59 were generally lower than H7 with AS03. With AS03, homologous and heterologous HAI seroprotection rates above 95% were seen with the 7.5 µg and the 15 µg dose groups, and homologous seroprotection responses of 94.6% were seen with the 3.75 µg dose. With MF59, the homologous HAI seroprotection responses seen with the highest dose (15 µg) were lower than the heterologous HAI seroprotection observed with the lowest dose of AS03 (3.75 µg). These findings highlight that even for immunogens considered poorly immunogenic, robust immune responses can be generated with lower antigen doses when delivered in a 2-dose series with a suitable adjuvant.

4.4 End of Study Definition

A participant is considered to have completed the study if he/she has completed the last contact planned in the SoA.

The end of the study is defined as the date of the last contact of the last participant in the study.

However, for periodic safety reports, the study is considered completed when the Clinical Study Report is finalized.

5 Study Population

Prospective approval of protocol deviations to recruitment and enrollment criteria, also known as protocol waivers or exemptions, is not permitted.

5.1 Inclusion Criteria

Participants are eligible for the study only if all of the following criteria are met:

- I01: Aged 18 years of age or older on the day of inclusion
- I02: Informed consent form has been signed and dated
- I03: Able to attend all scheduled visits and to comply with all study procedures

5.2 Exclusion Criteria

Participants are not eligible for the study if any of the following criteria are met:

E01: Participant is pregnant, or lactating, or of childbearing potential and not using an effective method of contraception or abstinence from at least 4 weeks prior to the first vaccination until at least 12 weeks after the last vaccination. To be considered of non-childbearing potential, a female must be post-menopausal for at least 1 year or surgically sterile.

E02: Participation at the time of study enrollment (or in the 30 days preceding the first study vaccination) or planned participation during the present study period in another clinical trial investigating a vaccine, drug, medical device, or medical procedure

E03: Receipt of any vaccine in the 30 days preceding the first study vaccination or planned receipt of any vaccine in the 30 days following the last study vaccination except for influenza vaccination, which may be received at least 2 weeks before and a minimum of 2 weeks after study vaccines.^a

E04: Prior administration of a coronavirus vaccine (severe acute respiratory syndrome coronavirus 2 [SARS-CoV-2], SARS-CoV, Middle East Respiratory Syndrome [MERS-CoV])

E05: Receipt of immune globulins, blood or blood-derived products in the past 3 months

E06: Known or suspected congenital or acquired immunodeficiency; or receipt of immunosuppressive therapy, such as anti-cancer chemotherapy or radiation therapy, within the preceding 6 months; or long-term systemic corticosteroid therapy (prednisone or equivalent for more than 2 consecutive weeks within the past 3 months)

E07: History of SARS-CoV-2 infection, confirmed either clinically, serologically^b, or microbiologically

E08: Known systemic hypersensitivity to any of the vaccine components, or history of a life-threatening reaction to a vaccine containing any of the same substances^c

E09: Self-reported thrombocytopenia, contraindicating intramuscular (IM) vaccination based on Investigator's judgment

E10: Bleeding disorder, or receipt of anticoagulants in the 3 weeks preceding inclusion, contraindicating IM vaccination based on Investigator's judgment

^a While receipt of any vaccine as listed in this criterion is exclusionary for this study, enrolled participants are free to receive an authorized/approved COVID-19 vaccine during the follow-up period. As efficacy has not been demonstrated for any of the investigational formulations under evaluation in the current study, it is not required to unblind participants to the VAT00001 study assignment prior to administration of an authorized COVID-19 vaccine. If the participant receives the authorized/approved vaccine, this information would be collected and the participant's data up to the point of receipt of authorized/approved vaccine will be included in the primary analysis for immunogenicity and safety. Participants will continue to be followed for the duration of the trial as per scheduled visits and procedures. (see [Section 7.1.2: Definitive Contraindications](#)).

^b Potential study participants will need to have a negative SARS-CoV-2 antibody test at time of enrollment.

^c The components of SARS-CoV-2 Recombinant Protein vaccine are listed in [Section 6.1](#) and in the SARS-CoV-2 Recombinant Protein Investigator's Brochure. In addition, information for the AF03 adjuvant are listed in the AF03 Investigator's Brochure.

E11: Deprived of freedom by an administrative or court order, or in an emergency setting, or hospitalized involuntarily

E12: Current alcohol abuse or drug addiction

E13: Chronic illness or condition considered to potentially increase the risk for severe COVID illness^a (26) or that, in the opinion of the Investigator, is at a stage where it might interfere with study conduct or completion^b

E14: Moderate or severe acute illness/infection (according to Investigator judgment) on the day of vaccination or febrile illness (temperature $\geq 38.0^{\circ}\text{C}$ [$\geq 100.4^{\circ}\text{F}$]). A prospective participant should not be included in the study until the condition has resolved or the febrile event has subsided

E15: Receipt of any therapy known to have in-vitro antiviral activity against SARS-CoV-2^c within 72 hours prior to the first blood draw

E16: Identified as an Investigator or employee of the Investigator or study center with direct involvement in the proposed study, or identified as an immediate family member (ie, parent, spouse, natural or adopted child) of the Investigator or employee with direct involvement in the proposed study

E17: Residence in a nursing home or long-term care facility

E18: Health care workers providing direct patient care for COVID-19 patients

E19: Participants with active or prior documented autoimmune disorder (such as potential immune-mediated diseases [pIMDs])

If the participant has a primary physician who is not the Investigator, the site should contact this physician with the participant's consent to inform him / her of the participant's participation in the study. In addition, the site should ask this primary physician to verify exclusion criteria relating to previous therapies, such as receipt of blood products or previous vaccines.

5.3 Lifestyle Considerations

No other restrictions than the ones listed in the exclusion criteria or in the contraindications for subsequent vaccinations are required.

^a Factors that may increase the risk of severe COVID illness include: autoimmune disease (see also [Appendix 10.5](#) for a list of potential immune-mediated medical conditions); cerebrovascular disease; chronic pulmonary disease (including asthma, chronic obstructive pulmonary disease, emphysema, cystic fibrosis, pulmonary fibrosis); current smoking or former smoking; current vaping; diabetes mellitus; cardiovascular disease (including hypertension); chronic renal disease; chronic liver disease; immunocompromised condition; neurologic disorder (including dementia); obesity (body mass index ≥ 30); sickle cell disease; thalassemia.

^b Chronic illness may include, but is not limited to, psychiatric disorders.

^c Therapy/treatment including, but not limited to, favipiravir, lopinavir/ritonavir, remdesivir, arbidol, chloroquine, hydroxychloroquine.

5.4 Screen Failures

Screen failures are defined as participants who consent to participate in the clinical study but are not subsequently randomly assigned to study intervention. Screening information is recorded in the source documents.

6 Study Intervention

Study intervention is defined as any investigational intervention(s), marketed product(s), placebo, or medical device(s) intended to be administered to a study participant according to the study protocol.

6.1 Study Interventions Administered

Study interventions are described in [Table 6.1](#).

Table 6.1: Identity of study interventions

CoV2 preS dTM-AF03		
Intervention Name	CoV2 preS dTM-AF03 (low-dose)	CoV2 preS dTM-AF03 (high-dose)
Study Groups	1 and 6	3 and 8
Use	Experimental	
Type	Vaccine	
Dose Formulation	Liquid, mix at bedside pre-injection according to dose preparation protocol	
Unit Dose Strengths	Each 0.5 mL dose of Study Intervention will contain the following: 
• preS-deltaTM monovalent: prefusion S delta TM COVID19 antigen, low-dose (5 µg)• preS-deltaTM monovalent: prefusion S delta TM COVID19 antigen, high-dose (15 µg)	
Excipients/Diluent	Each mono-dose vial of squalene-based AF03 adjuvant 2.5% contains: 
• Diluent: Phosphate-buffered saline (PBS)• Sorbitan monooleate (Dehymuls SMO™) (1.85 mg)• POE (12) Cetostearyl ether (Kolliphor CS12™) (2.38 mg)• Mannitol (2.31 mg)	
Dosage Level	0.5 mL per dose	
Number of Doses / Dosing Interval	Cohort 1 : 1 injection / Cohort 2 : 2 injections, 21 days apart	
Route of Administration	IM injection	
Site of Administration	Deltoid muscle in the upper arm	
Sourcing	Provided by the Sponsor	
Packaging and Labeling	Each study intervention will be provided in an individual box (antigen and adjuvant will be kitted together in a 2-vial box). Each study intervention (vial) will bear one fixed label and each box will bear detachable label(s) and one fixed label containing the dose number. All will be labeled as required per US requirement.	
Batch Number	TBD	

CoV2 preS dTM-AS03		
Intervention Name	CoV2 preS dTM-AS03 (low-dose)	CoV2 preS dTM-AS03 (high-dose)
Study Groups	2 and 7	4 and 9
Use	Experimental	
Type	Vaccine	
Dose Formulation	Liquid, mix at bedside pre-injection according to dose preparation protocol	
Unit Dose Strengths	Each 0.5 mL dose of Study Intervention will contain the following: 
 • preS-deltaTM monovalent: prefusion S delta TM COVID19 antigen, low-dose (5 µg) • preS-deltaTM monovalent: prefusion S delta TM COVID19 antigen, high-dose (15 µg) 	
Excipients/Diluent	Each multi-dose vial of squalene-based AS03 adjuvant 2.1% contains: 
 • Diluent: PBS • Tocopherol (antioxidant) (11.86 mg) • Polysorbate 80 (Tween®80) (4.86 mg) 	
Dosage Level	0.5 mL per dose	
Number of Doses / Dosing Interval	Cohort 1 : 1 injection / Cohort 2 : 2 injections, 21 days apart	
Route of Administration	IM injection	
Site of Administration	Deltoid muscle in the upper arm	
Sourcing	CoV preS dTM : Provided by the Sponsor AS03: Provided by GSK	
Packaging and Labeling	Each study intervention will be provided in an individual box (antigen and adjuvant will be kitted together in a 2-vial box). Each study intervention (vial) will bear one fixed label and each box will bear detachable label(s) and one fixed label containing the dose number. All will be labeled as required per US requirement.	
Batch Number	TBD	
CoV2 preS dTM		
Intervention Name	CoV2 preS dTM (high-dose)	
Study Groups	10 (18-49 years of age in Cohort 2 only)	
Use	Experimental	
Type	Vaccine	
Dose Formulation	Liquid, mix at bedside pre-injection according to dose preparation protocol	
Unit Dose Strengths	Each 0.5 mL dose of CoV2 preS dTM antigen (high-dose) will contain the following: 
 • preS-deltaTM monovalent: prefusion S delta TM COVID19 antigen, high-dose (15 µg) 	
Excipients/Diluents	Diluent : PBS	
Dosage Level	0.5 mL per dose	
Number of Doses / Dosing Interval	Cohort 1 : 1 injection / Cohort 2 : 2 injections, 21 days apart	

Route of Administration	IM injection
Site of Administration	Deltoid muscle in the upper arm
Sourcing	Provided by the Sponsor
Packaging and Labeling	Each study intervention will be provided in an individual box (antigen and diluent will be kitted together in a 2-vial box). Each study intervention (vial) will bear one fixed label and each box will bear detachable label(s) and one fixed label containing the dose number. All will be labeled as required per US requirement.
Batch Number	TBD
Placebo	
Intervention Name	Placebo
Study Groups	5 and 11
Use	Placebo - comparator
Type	Vaccine
Dose Formulation	Liquid, in a single-vial presentation
Unit Dose Strengths	0.9% normal saline
Dosage Level	0.5 mL per dose
Number of Doses / Dosing Interval	Cohort 1 : 1 injection / Cohort 2 : 2 injections, 21 days apart
Route of Administration	IM injection
Site of Administration	Deltoid muscle in the upper arm
Sourcing	Provided by the Sponsor
Packaging and Labeling	Each study intervention will be provided in an individual box similar to the kits used for other study interventions. Each study intervention (vial) will bear one fixed label and each box will bear detachable label(s) and one fixed label containing the dose number. All will be labeled as required per US requirement.
Batch Number	TBD

6.2 Preparation/Handling/Storage/Accountability

Detailed guidance and information are provided in the Operating Guidelines.

- 1) The Investigator or designee must confirm appropriate temperature conditions have been maintained during transit for all study intervention received and any discrepancies are reported and resolved before use of the study intervention.
- 2) Only participants enrolled in the study may receive study intervention and only authorized site staff may supply or administer study intervention. All study intervention must be stored in a secure, environmentally controlled, and monitored (manual or automated) area in accordance with the labeled storage conditions with access limited to the Investigator and authorized site staff.

- 3) The CoV2 preS dTM antigen will be mixed with the mono-dose vial of AF03 adjuvant, multi-dose vial of AS03 adjuvant, or PBS at the site prior to administration. Vaccine formulations will be prepared in the CoV2 preS dTM antigen vials by adding an equal volume of adjuvant (AF03 or AS03) or PBS.
- 4) The Investigator, institution, or the head of the medical institution (where applicable) is responsible for study intervention accountability, reconciliation, and record maintenance (ie, receipt, reconciliation, and final disposition records).
- 5) Further guidance and information for the final disposition of unused study interventions are provided in the Operating Guidelines.

6.3 Measures to Minimize Bias: Randomization and Blinding

6.3.1 Randomization and Allocation Procedures

On the day of enrollment, participants who meet the eligibility criteria and sign the Informed Consent Form (ICF) will be stratified by 2 age groups (18-49 years and ≥ 50 years) and then be randomly assigned to receive 1 injection (Cohort 1) or 2 injections (Cohort 2) of CoV2 preS DTM investigational study vaccine or placebo. As shown in [Table 4.2](#), within each cohort:

- participants aged 18-49 years:
 - will be randomized to 6 groups to receive Antigen Formulation 1 (low-dose [5 μ g]) with either AF03 or AS03 adjuvant; Formulation 2 (high-dose [15 μ g]) with either AF03, AS03, or no adjuvant; or placebo (Note: unadjuvanted arm included in Cohort 2 only)
 - N = 20 participants in each group, except for AS03-adjuvanted groups in Cohort 2 with 60 participants in each group
- participants aged ≥ 50 years:
 - will be randomized to 5 groups to receive Antigen Formulation 1 (low-dose [5 μ g]) or Formulation 2 (high-dose [15 μ g]) each with either AF03 or AS03; or placebo
 - N = 10 participants in each group, except for AS03-adjuvanted groups in Cohort 2 with 30 participants in each group

The study will initially enroll 30 participants (6 within each dosing group from Cohort 1) 18-49 years of age, who will comprise the Sentinel Safety Cohort. Participants in this cohort will receive 1 injection of study intervention to which they were randomized, and safety and laboratory parameters up to D09 will be evaluated. Upon demonstration of acceptable safety, the remaining participants in Cohort 1 and all participants in Cohort 2 will be enrolled and randomized.

A subset of 87 participants in Cohort 2 (60 participants 18-49 years of age [18 per group in AS03-adjuvanted vaccines; 6 per group in all other study groups]) and 27 participants ≥ 50 years of age [9 per group in AS03-adjuvanted groups; 3 per group in all other study groups, with the exception of the unadjuvanted group for which there will be no older adults]), will be randomly assigned to a cellular-mediated immune (CMI) subset.

Site staff will connect to the Interactive Response Technology (IRT), enter the identification, security information, and confirm a minimal amount of data in response to IRT prompts. The IRT will then provide the group assignment and have the site staff confirm it. The full detailed

procedures for group allocation are described in the Operating Guidelines. If the participant is not eligible to participate in the study, then the information will only be recorded on the participant recruitment log.

Participant numbers that are assigned by the IRT will consist of a 12-digit string (a 3-digit country identifier, a 4-digit study center identifier, and a 5-digit participant identifier). For example, Participant 840000100005 is the fifth participant enrolled in Center Number 1 in the US (840 being the US country code).

Participant numbers should not be reassigned for any reason. The randomization codes will be kept securely in the IRT system.

6.3.2 Blinding and Code-breaking Procedures

The study will be performed in a modified double-blind (observer-blind) fashion:

- Investigators and study staff who conduct the safety assessment and the participant will not know which vaccine is administered in order to decrease the risk of potential bias
- Only the study site staff who prepare and administer the vaccine and are not involved with the safety and efficacy evaluation will know which vaccine is administered
- Testing laboratories will be blinded

The code may be broken in the event of an AE only when the identification of the vaccine received could influence the treatment of the participant. Code-breaking should be limited to the participant(s) experiencing the AE.

The blind of individual participants can be broken by the Investigator or a delegate through the IRT system, as explained in the code-breaking procedures described in the Operating Guidelines. Once the emergency has been addressed by the site, the Investigator or a delegate must notify the Sanofi Pasteur RMO if a participant's code was broken. All contact attempts with the Sponsor prior to unblinding are to be documented in the source documents, and the code-breaking CRF is to be completed.

The Institutional Review Board/Independent Ethics Committee (IRB / IEC) must be notified of the code-breaking, in accordance with local regulations. All documentation pertaining to the event must be retained in the site's study records and in Sanofi Pasteur's files. Any intentional or unintentional code-breaking must be reported, documented, and explained, and the name of the person who requested it must be provided to the Sponsor.

A request for the code to be broken may also be made by the Global Pharmacovigilance (GPV) Department through an internal system for reporting to Health Authorities in the case of an SAE, as described in International Council for Harmonisation (ICH) E2A^a. In this case, the code will be broken only for the participant(s) in question. The information resulting from code-breaking (ie, the participant's vaccine or group assignment) will not be communicated to either the Investigator or the immediate team working on the study, except for the GPV representative.

The code-breaking procedures are described in the Operating Guidelines.

^a All unexpected and related SAEs submitted to European Union competent authorities must be unblinded.

The blind will be broken by the Sponsor at the time of the ESDR (with access to study intervention assignments [for the Sentinel Safety Cohort participants only] to a limited number of Sponsor Study Staff members comprising the Core Safety Management Team) and at the time of the first interim analysis after the first database lock. However, participant-level data will be maintained blinded on site until the end of the study/until the interim Clinical Study Report approval.

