future supply, in the event supply beyond AS03 capacity is possible with the recombinant protein and needed to address the pandemic; 3) the AF03 adjuvant may be of interest in the future if COVID-19 becomes seasonal, in which case a co-formulated vaccine would be attractive; in such circumstances, co-formulation with AF03 will be more feasible than with AS03 as both protein and adjuvant are proprietary to Sanofi Pasteur. The higher priority given to AS03 adjuvanted formulations and the higher likelihood of robust immune responses with a 2-injection schedule provides rationale to generate more precise data for AS03 formulations in Cohort 2 of this Phase I/II study; this is the justification for a sample size of 90 across age groups for the AS03 adjuvanted arms in Cohort 2. All other arms in the study will have a size of 30 total, except for the un-adjuvanted arm which would only comprise 20 younger adults.

Rationale for Blinding

This is an observer-blind study for formulation and adjuvant. Owing to the need for mixing of study formulations from separately supplied antigen, adjuvants, and / or diluent, the person preparing and administering the vaccine will be unblinded to vaccine group assignment. Blinding of all “observers” will minimize the risk of bias arising from the possibility of consciously or unconsciously influencing the reporting of study outcome measures due and knowledge of the formulation administered.

Rationale for Placebo

Placebo, rather than a benefit licensed vaccine, will be used for comparison to vaccine to allow safety comparisons between vaccine and placebo as there are no other licensed COVID-19 vaccines on the market. The inclusion of placebo groups will also maintain the blind, allowing the unbiased evaluation of clinical outcomes related to COVID-19-like illness and SARS-CoV-2 infection by treatment group (secondary efficacy objective).

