9.5 Interim Analyses

An interim analysis will be performed on data collected for primary immunogenicity and exploratory CMI objectives obtained up to D36 and primary safety data collected up to D43, upon the data availability and when a partial database lock has been conducted. Statistical analysis of data described above will be conducted to support formulation selection for further investigation. The analyses results will also be generated to communicate with regulatory agencies. The study blind will be broken at the group level to the Sponsor at that time.

After the 6-month data have been collected, a further interim analysis will be performed on immunogenicity, safety, and efficacy endpoints. The study blind will be broken at the group level to the Sponsor at that time. At the time of protocol Amendment 1, a partial database lock has been conducted.

A final analysis for all data collected will be conducted once the 12-month safety data have been collected and the final database lock has occurred.

The SAP will describe the planned interim analyses in greater detail.

Participant safety will be continuously monitored by the Sponsor's internal safety review committee which includes safety signal detection at any time during the study (see also [Section 8.4](#) for halting rules).

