5.4 Interim / Preliminary Analysis

An interim analysis will be performed on data collected for primary immunogenicity and exploratory CMI objectives obtained up to D36 and primary safety objectives obtained up to D43, upon the data availability and when a partial database lock has been conducted. Statistical analysis of data described in [Section 5.1.1](#) and [Section 5.1.3](#) (CMI analyses except the PCA analysis) will be conducted to support formulation selection for further investigation. The analyses results will also be generated to communicate with regulatory agencies. If sufficient efficacy data are available at this interim analysis, the assessment of early efficacy will be performed as described in [Section 5.1.2.4](#).

At the first interim analysis, an independent statistical group includes an independent statistician and an independent programmer will be unblinded at subject level to generate interim outputs including tables, listings, and figures. The treatment code will be masked from the interim outputs to ensure that subject-level unblinding is not available outside the independent statistical group. A group of study members will review the interim outputs unblinded at group level, to perform decision-making on dose-selection and generate the abbreviated clinical study report (CSR) and interim CSR. This group will include study statisticians and study programmers, clinical study leads, pharmacovigilance, Global Clinical Immunology project representatives, and medical writer. Study statisticians and programmers will validate and perform quality control of group-unblinded statistical outputs. Additionally, certain members of the project team and certain Sanofi Pasteur management will be consulted in the course of the formulation selection, and thus be aware of the group-level data. Regulatory personnel will communicate to CBER with interim

outputs and abbreviated CSR. In addition, any subject experiencing a SUSAR (Suspected Unexpected Serious Adverse Reaction) will be unblinded to pharmacovigilance or in case any condition is met as described in the protocol. Parties remaining blinded includes participants, lab analysts, site investigators, and study team other than specified above. Furthermore, the study team will remain blinded on data collected after date cut of the interim analysis.

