In the interests of transparency, it is the intention of Sanofi Pasteur to submit the results of the interim analysis to a peer-reviewed journal and/or pre-print server once the approval to begin the Phase III trial is received and ideally prior to the first enrollment of the Phase III trial. It is planned that all study investigators will be co-authors of this manuscript. Work on this manuscript will begin after the brief study report is submitted to CBER. As such, once these interim results are published, it will be widely known, including possibly to study participants and site staff.

For interim analyses specified below, the above unblinding process for functions in the Sponsor Study team will be the same. Dose-selection will apply only at the first interim.

After the 6-month data have been collected, a further interim analysis will be performed on all immunogenicity, safety, and efficacy endpoints. The study blind will be broken at the group level to the Sponsor at that time. At the time of protocol version 4.0, a partial database lock has been conducted.

A final analysis for all data collected will be conducted once the 12-month safety data have been collected and the final database lock has occurred.

Participant safety will be continuously monitored by the Sponsor's internal safety review committee which includes safety signal detection at any time during the study (see also Section 8.4 of the protocol for halting rules).

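### Protocol 6.3.2 gives two different end points for the site blind, and the earlier one would permit participant-level unblinding at sites during the 12-month follow-up

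*Protocol*

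**What the plan says.** Protocol 6.3.2 lists when the sponsor breaks the blind: at the early safety data review, for sentinel participants only, and "at the time of the first interim analysis after the first database lock". The next sentence qualifies this for the sites: "participant-level data will be maintained blinded on site until the end of the study/until the interim Clinical Study Report approval". A slash joins the two end points, with no rule for choosing between them.

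Protocol 9.5 bases the first interim on primary immunogenicity and exploratory CMI data "obtained up to D36 and primary safety data collected up to D43, upon the data availability and when a partial database lock has been conducted". What the sponsor learns is limited: "The study blind will be broken at the group level to the Sponsor at that time".

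SAP 5.4 has a defined group review the group-level outputs of that first interim "to perform decision-making on dose-selection and generate the abbreviated clinical study report (CSR) and interim CSR". On everyone else it says: "Parties remaining blinded includes participants, lab analysts, site investigators, and study team other than specified above". For the 6-month interim it adds: "For interim analyses specified below, the above unblinding process for functions in the Sponsor Study team will be the same". The SAP states no date on which the site blind ends.

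Protocol 4.2 justifies the placebo partly because it preserves the blind, "allowing the unbiased evaluation of clinical outcomes related to COVID-19-like illness and SARS-CoV-2 infection by treatment group".

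**The concern.** The two end points are months apart. A sponsor following the second could release participant-level assignments to sites once the interim report is approved, while primary safety follow-up continues.

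The data still accruing would be:

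- **Late safety.** SAEs, AESIs and MAAEs are collected throughout the study (Protocol 8.4.1), and the investigator judges causality of unsolicited systemic events (Protocol 10.3.3). Safety to 12 months after the last injection is a primary objective, and SAP 5.1.1.2 includes a pooled placebo group among its summaries.
- **COVID-19-like illness.** A respiratory sample is triggered by symptoms. Active calls stop at D181 or D202, after which surveillance is passive (Protocol 8.2.2.2).
- **Outside vaccination.** Participants may take an authorized vaccine at any time, and their later data are only listed (SAP 5.1). Someone who learns that they received placebo has more reason to do so early, so the length of follow-up analysed could come to differ by arm.

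In each case, knowledge of assignment could change behaviour or judgement differently between vaccine and placebo arms.

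**Working it through.** **1. Which report the sentence refers to.** In 6.3.2 it directly follows the mention of the first interim analysis. SAP 5.4 names an interim CSR as a product of that same interim. The natural reading is therefore the report on data to D36/D43. The 6-month report is a possible alternative, and both are worked below.

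**2. Inputs.** The last visit is D366 (Cohort 1) or D387 (Cohort 2). The first-interim safety cut is D43. The 6-month visit is D181 or D202. All are in the schedules of activities and Protocol 9.5.

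**3. Reproducing the stated durations.** 366 − 1 = 365 days and 387 − 1 = 386 days, which match the totals in the Protocol synopsis.

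**4. Share of a participant's follow-up still to come when sites could be unblinded.**

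Share = (last day − 43 − lag) / total days, where lag is the time from that participant's D43 to approval of the report. Neither document gives an approval date, so the lag is an assumption, varied from 0 to 240 days.

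| Assumed lag after D43 | Cohort 1 | Cohort 2 |
|---|---|---|
| 0 days | 323/365 = 0.8849 (88%) | 344/386 = 0.8912 (89%) |
| 60 days | 263/365 = 72.1% | 284/386 = 73.6% |
| 120 days | 203/365 = 55.6% | 224/386 = 58.0% |
| 180 days | 143/365 = 39.2% | 164/386 = 42.5% |
| 240 days | 83/365 = 22.7% | 104/386 = 26.9% |

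The share passes one half at a lag of 323 − 365/2 = 140.5 days (Cohort 1) or 344 − 386/2 = 151 days (Cohort 2).

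**5. If the 6-month report is meant.** (366 − 181)/365 = 185/365 = 50.7%, and (387 − 202)/386 = 185/386 = 47.9%. These are maxima, before any reporting lag.

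**6. If the end of the study governs.** Protocol 4.4 defines it as the last contact of the last participant, so the share is 0%.

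**7. Which endpoints fall in the exposed period.** Immediate, solicited and 21-day unsolicited events and the safety laboratory tests are complete by D43, so they are not affected. SAEs, AESIs, MAAEs and COVID-19-like illness continue to D366/D387 and are. Serologically confirmed infection rests on anti-N ELISA at scheduled visits in all participants through the last visit (Protocol Table 8.1), so finding it does not depend on anyone reporting symptoms.

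**The case against.** The strongest reply is that this is loose wording with little practical effect. Several parts of it stand.

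- **The conflict with the SAP is by implication.** A reader might infer a flat contradiction. SAP 5.4 says who stays blinded at the interims but sets no end date for sites. Protocol 9.5 describes what the sponsor sees and does not mention sites.
- **Release is permitted, not scheduled.** A reader might infer that sites could unblind themselves. The documents do not support that: codes are held in the IRT system (Protocol 6.3.1), and a site code-break is confined to an adverse event whose treatment could depend on the assignment (Protocol 6.3.2).
- **Some safeguards remain.** Virologically confirmed illness needs a positive NAAT, calls run every two weeks to D181/D202, and the sponsor also assesses causality of SAEs and non-serious AESIs. A reader might infer that all COVID-19 endpoints are compromised, but scheduled anti-N testing largely protects the serological one.
- **The analyses are descriptive** (Protocol 9.1), and the final efficacy analyses might not be run (SAP 5.1.2.4 and 5.7). No comparison of time to censoring is planned, so a claim of bias in one would have nothing to attach to.
- **The blind was never complete.** Injection schedule is open, and those preparing and giving injections are unblinded.

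These points narrow the issue without removing it. Preparers and administrators are separated from safety and efficacy evaluation. The blind at stake is that of observers and participants, and the arm-by-arm description of late safety remains a primary analysis. A written permission to release is enough to matter. The SAP's silence on an end date means that neither document settles the question.

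**Conclusion.** The point holds: Protocol 6.3.2 has two incompatible end points for the site blind. The earlier one would permit unblinding at sites during follow-up, in tension with the stated purpose of the placebo and, by implication, with SAP 5.4.

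A reader might infer that most of follow-up would be open-label. The documents do not establish that. It requires the first-interim report to be the one meant, and approval within about 140 days (Cohort 1) or 151 days (Cohort 2) of a participant's D43. A zero lag is an upper limit, since locking, analysis and reporting must come first, and early enrollees have longer lags than late ones. Nor is the roughly one-half figure for the 6-month report a lower limit: a 240-day lag after D43 leaves about a quarter.

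The exposure is to late SAEs, AESIs and MAAEs, symptom-triggered illness, and the timing of outside vaccination. The case for correction does not depend on the exact share. It should be made because the rule as written allows avoidable bias in a primary safety objective.

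**What to change.** In Protocol 6.3.2, delete the slash and the words after it, leaving one end point. Participants, investigators, site assessors and laboratories would then stay blinded at participant level until the end of the study as defined in Protocol 4.4. State the same end point in SAP 5.4. The existing emergency and SUSAR code-breaks stay as they are.

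This deletion does not carry the blind to final database lock, which neither document sets as the end point for sites.

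If release at an interim report was intended, 6.3.2 should name which report, and the SAP should present site-assessed data collected after it as open-label.

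The cost is one phrase removed from the protocol and one sentence added to the SAP, by amendment or clarification, with no new procedures.
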